1.4 Selection of Drugs and Dosages

Both NS and LR are available with identical storage volumes and dosing strategies.

For this study, standard storage units of NS and LR will be used, including 250, 500, and 1,000 mL units. At the discretion of the care team, dextrose may be added to either NS or LR for resuscitation (uncommon) or maintenance (common) fluid therapy. Commonly used dextrose preparations for pediatric septic shock include NS or LR with 5% or 10% dextrose which are also available in standard volumes of 250, 500, and 1,000 mL units. Potassium or other electrolytes may be added to either NS or LR as clinically indicated.

Volume for fluid resuscitation is typically 10-20 mL/kg per dose administered over 5-20 minutes via the intravenous or intraosseous route, though children with sepsis often receive >100-200 mL/kg total crystalloid volume resuscitation within 24-48 hours. Volume for maintenance fluids is typically determined by patient weight, assessment of intravascular volume status, and need for a specific glucose infusion rate. However, for this study, only the type of base fluid (i.e., NS or LR) will be determined by study protocol, while the actual volume administered (per bolus dose, per hour, and in total), duration of administration, and need for electrolyte additives (i.e., dextrose, potassium, others) will be at the complete discretion of the treating care team.

The costs for NS and LR are equivalent, with both fluids at approximately \$1-2.00 per liter. Since the volume of fluid will be determined by the care team and use of both NS and LR are consistent with published guidelines for crystalloid resuscitation of pediatric septic shock, the randomized selection of fluid will not significantly alter health care costs for subjects enrolled in this study.

Both NS and LR are FDA-approved crystalloid fluid solutions recommend for use^{10,12} and clinically used for resuscitation of patients with shock.¹³⁻¹⁵ NS was first approved for medical use by the FDA in 1970, and LR was first approved for medical use by the FDA in 1971. Both NS and LR are listed for use in pediatrics based on “clinical practice” and reference in the “medical literature”. In the pediatric ED population, however, NS is overwhelmingly the more common fluid used for resuscitation of pediatric septic shock.¹⁵ Therefore, we will consider NS to be the control fluid (since >98% of patients not enrolled in this study would initially receive NS) and LR, the less commonly utilized fluid, the intervention fluid in this study. Specific cautions for use of LR in the pediatric and critically ill population are shown in Table 2:

Table 2: FDA Contraindications and Warnings to LR Administration to the Pediatric and Critically Ill Population

Concern	Type of Caution	Relevance to Proposed Study
Pediatric Population:		
LR and ceftriaxone must not be simultaneously	Contraindication	Not relevant, inclusion criteria are age >6 months to <18 years (see page 11, section 3.4.1)

administered (age \leq 28 days)		
LR and ceftriaxone must not be simultaneously administered through the same infusion line (age >28 days)	Contraindication	If both LR and ceftriaxone prescribed, usual, routine clinical practice will be followed (see page 10, section 3.1.2)
Lactate-containing solutions should be administrated with caution to infants <6 months	Warning	Not relevant, inclusion criteria are age >6 months to <18 years (see page 11, section 3.4.1)
Critically Ill Population:		
LR should not be simultaneously administered with citrate anticoagulated blood through same administration set	Warning	If both LR and blood products are administered, usual, routine clinical practice will be followed (see page 10, section 3.1.2)
LR infusion must be stopped if suspected hypersensitivity develop	Warning	Usual, routine clinical practice will be followed (see page 10, section 3.1.2)
Depending on volume and rate of infusion, infusion of LR can cause fluid overload and/or electrolyte abnormalities	Warning	Not relevant, volume and rate of infusion of both LR (and NS) are at the discretion of the clinical team and both fluid and electrolytes will be monitored as indicated as part of usual, routine clinical practice (see page 10-11, section 3.2.1)
Cautious administration of LR to patients with hyperkalemia or cardiac disease	Warning	Eligibility criteria require treating clinician to determine it is safe to administer both NS and LR (see page 11, section 3.4.1), with known hyperkalemia a specified exclusion criteria. In addition, study fluid may be stopped at clinician's discretion if new data changes this determination during intervention phase (page 11, section 3.1.2)
Cautious administration of LR to patients with metabolic alkalosis	Warning	Not relevant, metabolic alkalosis rare during resuscitation in septic shock and study fluid may be stopped at clinician's discretion (page 11, section 3.1.2)
Cautious administration of LR to patients with inability to metabolize lactate (e.g., fulminant hepatic failure)	Precaution	Although fulminant hepatic failure or complete inability to metabolize lactate is rare in septic shock, eligibility criteria require treating clinician to determine it is safe to administer both NS and LR with known fulminant hepatic failure a specified exclusion criteria (see page 11, section 3.4.1). In addition, study

		fluid may be stopped at clinician's discretion if new data changes this determination during intervention phase (page 11, section 3.1.2)
Cautious administration of LR to patients with hypercalcemia	Precaution	Although severe hypercalcemia is rare in pediatric septic shock, eligibility criteria require treating clinician to determine it is safe to administer both NS and LR (see page 11, section 3.4.1) with known hypercalcemia a specified exclusion criteria. In addition, study fluid may be stopped at clinician's discretion if new data changes this determination during intervention phase (page 11, section 3.1.2)

1.5 Relevant Literature and Data

Infusion of saline to restore circulating blood volume was first attempted during the cholera outbreak of the 1830's. In a letter to the *Lancet* published on June 2, 1832, Thomas Latta noted with intravenous saline "*improvement in the pulse and countenance is almost simultaneous, the cadaverous expression gradually gives place to appearances of returning animation, the livid hue disappears, the warmth of the body returns.*"⁴² Fluids of various composition were subsequently described, with the first reference to a solution similar to that of NS in the 1880's. Hartog Joakob Hamburger recognized that erythrocytes did not lyse when placed in NS and concluded that "the blood of man was isotonic with a NaCl solution of 0.9%".⁴³ Although these observations conceivably led to the "normal" moniker for 0.9% NS (nobody knows for sure), human plasma is actually closer to 0.6% NaCl. Subsequent events leading to the widespread adoption of NS into clinical practice remain unclear. LR was also born in the 1880's when Sydney Ringer added calcium and potassium to saline after observing that inorganic constituents of pipe water better preserved frog heart muscle *ex vivo* than just salt dissolved in distilled water.⁴⁴ In 1932, the pediatrician Alexis Hartmann modified Ringer's original formula in order to reduce the acidosis observed in infants with diarrhea.⁴³

Although commonly used, an increasing body of literature now links the high chloride content and low SID of NS to acute kidney injury (AKI), acidemia, hyperkalemia, vascular permeability, inflammation, coagulopathy, fluid overload, and death.²⁵ In particular, when infused in large volumes—as is common in septic shock—NS induces a hyperchloremic metabolic acidosis due to the dilution of plasma bicarbonate within a constant carbon dioxide environment in the absence of an alternative buffer.⁴⁵ In blood with normal protein levels, the SID (abbreviated $\text{Na} + \text{K} - \text{Cl}$) is approximately +40 mEq/L. Infusion of NS with a SID of 0 ($154 \text{ Na} + 0 \text{ K} - 154 \text{ Cl}$) produces an acidemia.⁴⁶ Such a hyperchloremic metabolic acidosis is pro-inflammatory in cell culture experiments²⁷ and has been associated with mortality following non-cardiac surgery.³⁰ Moreover, since acidemia is often attributed to tissue hypoperfusion in shock, a low blood pH following NS resuscitation may propagate

a feed-forward cycle of excessive fluid administration and volume overload, which itself has been associated with adverse clinical outcomes in multiple adult and pediatric studies.

However, despite suggestive relative efficacy and safety for balanced fluids like LR over NS for resuscitation of pediatric septic shock, whether there is a benefit for either NS or a more balanced fluid strategy remains unproven, particularly for pediatric septic shock. Because crystalloid fluids are so commonly used, even a small relative benefit of one fluid resuscitation strategy could provide a substantial public health impact. Unfortunately, because of unique pathophysiology and epidemiology for pediatric versus adult septic shock, results from ongoing adult fluid trials are unlikely to be generalizable to pediatric patients. Given both types of fluids are inexpensive, stable at room temperature, commonly used, have identical storage and dosing volumes, and are of proven clinical benefit, crystalloids fluids provide the ideal scenario for a large pragmatic comparative effectiveness trial. The proposed pilot study will address the specific feasibility concerns necessary to next perform a larger trial that will definitively determine the comparative effectiveness of NS versus LR in pediatric septic shock.

Enrollment of patients as close to the initiation of fluid resuscitation is critical, and the lack of early enrollment has been a major criticism of previous fluid resuscitation trials in adult studies.^{22,23} In the United States, the majority of children begin fluid resuscitation in the emergency department in which the therapeutic goal is generally to achieve hemodynamic stability prior to transfer to an inpatient setting, including the intensive care unit. Consequently, fluid resuscitation with volumes up to (and exceeding) 80 mL/kg commonly occur in the pediatric ED. Delaying enrollment of patients until after admission to an intensive care unit, thus, risks substantial volume of pre-study fluid resuscitation that may dilute the main effect of a specified fluid intervention. Such contamination with pre-study fluid resuscitation has been a primary criticism of previous sepsis studies focusing on adults admitted to an ICU, in which receipt of a mean fluid volume of 2000 mL prior to study enrollment has been reported in several studies.^{22,23} Therefore, enrollment of children with suspected septic shock in the ED setting as close to initiation of fluid resuscitation as possible is necessary to maximize the potential differential effect of NS versus LR fluid.

1.6 Compliance Statement

This study will be conducted in full accordance with all applicable Children's Hospital of Philadelphia Research Policies and Procedures and all applicable Federal and state laws and regulations including 45 CFR 46, 21 CFR Parts 50, 54, 56, 312, and 314. We will also follow the Good Clinical Practice: Consolidated Guideline approved by the International Conference on Harmonization (ICH) except for a limited scope and timeframe for monitoring clinical adverse events (AEs) given the comparative effectiveness nature of the proposed study involving two interventions with routine clinical use in pediatric sepsis and well-documented efficacy and safety profiles of both NS and LR.

The investigators will perform the study in accordance with this protocol, will obtain consent when possible, and will report unanticipated problems involving risks to subjects or others in accordance with The Children's Hospital of Philadelphia IRB Policies and Procedures and all federal requirements. Collection, recording, and reporting of data will be

accurate and will ensure the privacy, health, and welfare of research subjects during and after the study.

2 STUDY OBJECTIVES

The purpose of the proposed pilot study is to determine the feasibility of performing a large, pragmatic, randomized, open-label trial comparing the clinical effectiveness and safety of fluid resuscitation with NS versus LR for pediatric septic shock.

2.1 Primary Objective (or Aim)

The primary objective of this study is to determine compliance with study fluid administration, throughout the intervention phase, within each randomized arm using a pragmatic study design.

Specifically, we will determine if the proposed study design is feasible to provide a clinically important difference in crystalloid fluid type between the two study arms by measuring the proportion of intravenous crystalloid fluid administered as 0.9% saline for pediatric patients with suspected septic shock randomized to fluid resuscitation with either saline or lactated Ringer's.

2.2 Secondary Objectives (or Aim)

The secondary objectives are to:

- Estimate the proportion of eligible pediatric patients with suspected septic shock who may be enrolled into a large randomized pragmatic trial of fluid resuscitation with saline versus lactated Ringer's.
- Demonstrate feasibility of patient enrollment into a pragmatic fluid resuscitation trial using Exception from Informed Consent (EFIC).

3 INVESTIGATIONAL PLAN

3.1 General Schema of Study Design

The overall design for this pilot study is a randomized, open-label pragmatic clinical trial of two different crystalloid fluids to resuscitate pediatric septic shock. The two arms include 0.9% “normal” saline (NS; control arm) and lactated Ringer’s (LR, intervention arm). See Figure 1 for an overview of the study design and outcome assessment.

3.1.1 Screening Phase

Potential subjects will be referred by the treating team in the ED, but a member of the study team will perform final screening for eligibility based upon the protocol inclusion and exclusion criteria prior to enrollment of the subject. Triggers for potential enrollment to be considered by the treating team will include initial fluid resuscitation with at least 20 mL/kg intravenous (IV)/intraosseous (IO) crystalloid fluid for clinical concern for septic shock. To ensure rapid and appropriate eligibility and enrollment, ED staff (including ED attendings and fellows) will be included as study co-investigators and be trained regarding study enrollment criteria and procedures.

When time permits, parental/guardian permission (informed consent) will be obtained prior to any study related procedures being performed. However, under most circumstances, the life-threatening nature of septic shock and the narrow therapeutic window for fluid resuscitation (on the order of minutes after presentation and shock recognition) will preclude sufficient time for an appropriate discussion of the study to properly seek informed consent and assent. In these cases, enrollment will proceed under the conditions of “exception from informed consent” (EFIC) with notification of the subject’s legally authorized representative (LAR) as described in Section 9.6.3.

3.1.2 Intervention Phase

The intervention to be tested is fluid resuscitation with LR compared to the “usual practice” control fluid of NS. Other than prescribing which crystalloid fluid to use, the intervention will be purposely implemented without intense efforts to standardize timing and volume of fluid resuscitation or other components of clinical care.

The proposed interventional plan is that, prior to receipt of >40 mL/kg of crystalloid bolus fluid, eligible patients will be randomized to receive either NS or LR for all remaining fluid administration (bolus and maintenance) for up to 48 hours. The study period will end at 11:59pm on the calendar day following randomization such that all patients receive at least 24 hours of study fluid, which is the time-window from presentation in which most fluid resuscitation is completed for septic shock.²⁷ This time point for terminating the intervention phase was selected because it provided a pragmatic endpoint that can be used by clinicians to signal the point at which to cease study fluid administration. Selective fluid administration has been previously shown to result in widely different amounts of saline use,⁴⁷ though application of these findings in adults using a different allocation strategy to the one proposed for our study is not clear. Study fluids will not be blinded due to costs and interventions that are not in keeping with a simple, pragmatic trial and based on results from the previously published SPLIT fluid trial in which two-thirds of clinicians correctly

NOTE: Because LR should not be administered simultaneously with citrate anticoagulated blood through the same administration set, teams will be educated to follow usual, routine clinical practice for administration of LR with blood products. Clinical staff will be targeted for education about safe administration of LR with blood products prior to and throughout the study.

NOTE: Both NS and LR pose risk of a hypersensitivity reaction during IV/IO infusion. Teams will be educated to following usual, routine clinical practice for discontinuation of administration of study fluid if signs and/or symptoms of hypersensitivity reaction develops.

3.1.3 Follow-up Phase

After 11:59 pm on the calendar day following randomization, no further study fluid will be administered solely for research purposes and all care, including any subsequent crystalloid

fluid administration, will be at the discretion of the clinical team. The follow-up phase will continue for the duration of the hospitalization or up through 90 days following study enrollment, whichever comes first. Final determination of subject study completion versus withdrawal, as well as assessment of vital status and clinical outcomes will occur at hospital discharge or 90 days following study enrollment, whichever comes first.

3.2 Allocation to Treatment Groups and Blinding

Randomization will be performed using 1:1 permuted blocks. Randomization sequence will be generated prior to the start of the study and will be filed using a series of numbered, opaque envelopes. Envelopes with study arm assignment will be stored in close proximity to crystalloid fluids in the CHOP ED. Treatment allocation will be revealed to the clinical care team after eligibility for enrollment has been determined to be appropriate by asking a member of the care team to open the next sequentially numbered envelope. The number of the envelope and study arm assignment will be recorded in a log after opening the envelope. The clinical team will then be directed to use the assigned study fluid for all subsequent crystalloid fluid administration within the remainder of the study window. Compliance with study fluid administration will be the primary feasibility assessment in this study (Aim 1).

Fluid administration will be open-label and neither the subject nor the care team will be blinded to the allocated treatment assignment. Blinding study fluid is not pragmatic and unlikely to even be possible. In the SPLIT fluid trial, two-thirds of clinicians correctly identified the randomized crystalloid patients received as electrolyte differences following NS or LR provide clear indication of fluid selection.³⁵ However, randomization following study enrollment will help to minimize selection bias that might occur due to pre-enrollment awareness of study group assignment.

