4 STUDY PROCEDURES

4.1 Screening Visit

Patients will be screened at arrival to the ED (i.e., at ED triage) and continuously throughout the ED course for presence of eligibility criteria. Referrals for potential subject enrollment will be made by the ED care team if there is clinician concern for septic shock and need for crystalloid fluid resuscitation assessed by the care team. Although all members of the ED care team may participate in subject referral, a member of the study team will review and concur with the treatment team's eligibility assessment prior to enrollment of the subject. To ensure rapid and appropriate eligibility and enrollment, ED staff (including ED attendings and fellows) will be included as study co-investigators and be trained regarding study enrollment criteria and procedures. Once patients are determined to be eligible, the following study procedures will occur:

- Informed Consent (if time permits) or determination of EFIC
- Randomization

In addition, review of the daily ED triage logs and use of the ED sepsis pathway order set will be performed by study staff to determine potentially eligible patients who were not enrolled. The reason for non-enrollment for all eligible patients will be determined by querying the attending physician of record and/or relevant members of the clinical care team.

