6.3.2 Feasibility Analysis

The primary analysis will be based on an intention-to-treat approach and will include all subjects randomized whether or not study fluid was administered.

The primary endpoint will be defined as meeting feasibility criteria if either of the following criteria are met:

- 3) There is an absolute difference in the mean use of NS between arms of at least 65% with a lower 95% CI border of >60%. For example, feasibility criteria would be met if 90% of crystalloid fluid in the NS arm was NS compared to only 25% in the LR arm. The proportion of NS use in each arm will be compared using the chi-squared test with a 95% bootstrap confidence interval with bias correction (assuming skewed distribution of data) around the difference in the proportion of NS use in each arm.
- 4) At least 85% of subjects in the NS arm receive $\geq 90\%$ of study fluid as NS during the study window *and* at least 80% of subjects in the LR arm receive $\geq 75\%$ of study fluid as LR.

The secondary endpoints will be defined as meeting feasibility criteria if:

- The mean proportion of total crystalloids administered as non-study fluid (i.e., cross-over) is $\leq 25\%$ in each arm (for example, $\leq 25\%$ of total crystalloid is administered as NS for patients randomized to the LR arm).
- The proportion of eligible patients treated in the pediatric ED who are enrolled, randomized, and treated with study fluid is $>65\%$.
- EFIC is approved by the IRB at CHOP
- The proportion of eligible patients who meet criteria for EFIC who are not enrolled or who are enrolled but withdraw prior to completion of the follow-up phase is $\leq 10\%$.

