9 STUDY ADMINISTRATION

9.1 Treatment Assignment Methods

9.1.1 Randomization

Prior to enrollment of any subjects, a complete randomization scheme will be completed using a 1:1 permuted blocks. The randomization sequence will be filed within a series of sequentially numbered, opaque envelopes. A supply cart with both NS and LR will be available where the randomization envelopes are located and will be immediately available for enrollments, so as not to delay treatment of subjects. While not specifically a goal of this study, we do anticipate that the presence of the supply cart may actually enhance the speed of treatment since the fluid will be immediately available at the bedside.

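### No entry ties a child to an envelope before the arm is seen, so an assignment rejected at opening can leave the intention-to-treat set and raise measured compliance

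*Combined protocol and SAP*

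**What the plan says.** Section 3.2 (Allocation to Treatment Groups and Blinding) describes an open-label trial with a permuted-block sequence prepared in advance. Section 9.1.1 adds: "The randomization sequence will be filed within a series of sequentially numbered, opaque envelopes". The envelopes are kept near the fluids in the ED. Once eligibility is settled, allocation is revealed by "asking a member of the care team to open the next sequentially numbered envelope". Section 3.2 then states: "The number of the envelope and study arm assignment will be recorded in a log after opening the envelope".

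These two sections are the only descriptions of the procedure. They name envelope number and arm as log items. They do not mention a subject identifier, a time, an entry made before opening, sealing of the envelopes, or a later check of envelopes against the sequence.

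Section 6.3.2 defines the primary analysis as intention-to-treat; it "will include all subjects randomized whether or not study fluid was administered". The primary endpoint (6.1) is the share of crystalloid given as saline in each arm, which measures compliance with assignment.

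Several controls surround the procedure:
- Before enrollment, "a member of the study team will perform final screening for eligibility" (3.1.1). The same section says that "ED staff (including ED attendings and fellows) will be included as study co-investigators".
- Study staff review daily triage logs and use of the sepsis order set "to determine potentially eligible patients who were not enrolled" (4.1), and ask the attending or care team for the reason.
- Random chart audits cover enrollment of eligible subjects and crossover volume (3.1.2).
- Monitoring begins with full verification of recorded data (9.4.1).
- A master list links identities to study data (9.2).

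**The concern.** Allocation concealment protects against choosing the child with knowledge of the arm. It does not protect against discarding the child after the arm is seen. That needs a record, made before opening, that this child holds this envelope, and the documents describe none.

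Suppose a clinician opens an LR envelope and decides not to proceed. If the envelope is used for the next child, the numbering stays intact. The first child then appears in the 4.1 review as eligible but not enrolled, with the reason supplied by the clinicians involved. Under 6.3.2 that child should have been counted as randomized to LR and non-compliant.

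In most trials this would be a modest risk to the balance between arms. Here it bears on the endpoint itself, because a rejection at opening is the kind of event Aim 1 exists to count. If it happens, it is more likely in the LR arm: 1.4 says that more than 98% of patients outside the study would initially receive NS.

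**Working it through.** **Inputs.** 35 subjects per arm (6.4). Criterion 2 in 6.3.2 requires at least 85% of the NS arm and at least 80% of the LR arm to be adequately treated. 0.85 × 35 = 29.75, so the NS limb needs 30. 0.80 × 35 = 28, so the LR limb needs 28. Planning rates in 6.4 are about 90% for NS and about 89% for LR (using half-normal saline in an earlier trial as the proxy).

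**The plan's own figure.** 6.4 gives about 80% power for criterion 2, by simulation. With exact binomial tails and independent arms, the printed rates give P(X ≥ 30 | 35, 0.90) × P(X ≥ 28 | 35, 0.89) = 0.868 × 0.967 = 0.839. The printed NS rate is for a cut-off of at least 85% NS, whereas the criterion uses at least 90%, so the relevant rate cannot be higher. If it were 0.89 to 0.895, the product would be 0.791 to 0.816. The stated 80% is compatible with the text but cannot be reproduced exactly from it. The point here does not depend on it.

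**A single case.** 27/35 = 77.1% fails the LR limb. If one rejected child is unlogged and the envelope goes to a child who is adequately treated, 28/35 = 80.0% passes.

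**Pass probability of the LR limb.** Let X ~ Binomial(35, p) and let up to k inadequate subjects be replaced by new draws at the same p.
- k = 1: P(X ≥ 28) + P(X = 27)·p
- k = 2: P(X ≥ 28) + P(X = 27)·[1 − (1 − p)²] + P(X = 26)·p²

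At p = 0.75:
- k = 1: 0.3223 + 0.1520 × 0.75 = 0.436
- k = 2: 0.3223 + 0.1520 × 0.9375 + 0.1520 × 0.5625 = 0.550

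At p = 0.89:
- k = 1: 0.9667 + 0.0217 × 0.89 = 0.986
- k = 2: 0.9667 + 0.0217 × 0.9879 + 0.0080 × 0.7921 = 0.995

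| True LR adequacy p | none replaced | up to 1 | up to 2 |
|---|---|---|---|
| 0.75 (assumed) | 0.322 | 0.436 | 0.550 |
| 0.80 (assumed) | 0.599 | 0.716 | 0.809 |
| 0.89 (planned, 6.4) | 0.967 | 0.986 | 0.995 |

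**Criterion 2 as a whole.** The NS limb must also pass. Multiplying by 0.868, the value at the printed NS rate, gives 0.28, 0.38 and 0.48 at p = 0.75, and 0.84, 0.86 and 0.86 at p = 0.89.

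**Criterion 1.** Aim 1 can be met through the difference in mean NS use instead. One child in 35 moves the LR-arm mean by at most 1/35 = 2.9 percentage points, and two by at most 5.7.

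**Do the existing controls restore the child to the analysis?**
- The study-team eligibility check comes before opening, and treating physicians may themselves be the co-investigators who do it.
- The 4.1 review should find the child, but as a non-enrollment.
- The 3.1.2 audits are random and are not described as covering envelopes.
- The 9.4.1 verification covers what was recorded, so an unrecorded opening is outside it.
- The 9.2 master list is not said to hold envelope numbers.
- A gap in numbering shows a missing envelope but not whose it was, and reuse leaves no gap.

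**The case against.** The strongest reply is that such a child does not vanish. Eligibility screening and the consent or EFIC determination come before randomization, so the child has normally been identified for the study. The daily review and the reason sought for every eligible non-enrollment should then bring the child up. A reader might infer that an assignment can be dropped without trace. The documents do not support that: there is a trace, though it depends on the clinicians' account and carries the wrong label.

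A reader might also infer that the log holds nothing beyond number and arm, or that the intention-to-treat set cannot be verified. Both go too far. Section 3.2 names two items without excluding others, and log columns are often kept in operating procedures. What can be said is that no verification step is described. Recording the arm after opening is not a fault either, since the arm is unknown until then.

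The motive may be weak. Children are enrolled only if neither fluid is judged unsafe (3.4.2), and study fluid may be stopped openly afterwards (3.1.2, 4.6). LR is already about half of resuscitation fluid for septic shock in this hospital's PICU (7.1.2). These points stand, and they make frequent dropping unlikely.

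It can also be said that a dropped child counts against Aim 2. That is true, but Aim 2 counts only children who were treated with study fluid. A child rejected at opening and given none fails Aim 2 under either label, so Aim 2 neither deters the misclassification nor corrects Aim 1.

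Finally, at the planned 89% adequacy the shift in the LR limb is under 3 percentage points. That is correct, and it limits the severity.

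**Conclusion.** The point holds as a gap in the described procedure. Nothing in the documents shows that assignments were or would be dropped. The protocol does not say which act makes a child randomized, does not tie that act to a child before the arm is visible, and describes no reconciliation. The possible bias in Aim 1 is upward.

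Its size depends on two unknowns: how many children are dropped, for which the documents give no figure, and true LR adequacy. At the planned 89%, one or two replacements hardly matter (0.967 to 0.986 or 0.995). At an assumed 75%, where the LR arm should usually fail, they raise the chance of passing that limb from 0.32 to 0.44 or 0.55. The distortion is therefore largest when compliance is poor, which is when a feasibility study most needs a true answer. These figures describe the LR limb only. They are not the probability that the overall Aim 1 conclusion changes, because criterion 2 also needs the NS limb and criterion 1 is an alternative route.

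This is a cheap improvement for a single-site pilot, not a defect that invalidates it.

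**What to change.** - Amend 3.2 so that subject identifier, date and time are written in the log and on the sealed envelope before it is opened, with the arm added afterwards. State in 3.2 and 9.1.1 that the envelopes are sealed.
- State in 3.2 and 6.3.2 that a child counts as randomized from the pre-opening entry and stays in the intention-to-treat set whatever fluid follows.
- Keep all opened envelopes. Have the site study staff, or the compliance monitor already named in 9.4.1, reconcile envelopes, log, the 4.1 screening review and CRFs, and report any envelope opened out of sequence or without a matching subject. This should not fall to the data coordinating center, whose role 3.3.2 limits to receiving a limited dataset.

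The cost is a few seconds at the bedside, short edits to the protocol and a brief reconciliation listing. No additional patients are needed. Measured compliance may be slightly lower, because rejected assignments would then be counted.
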